5.2.1. Analyses for Binary Data

For analyses where treatment comparisons are relevant, binary data at each scheduled visit will be analyzed by two approaches: (1) the test of hypothesis (and the p-value) between two pairwise treatment groups will be conducted by the Cochran-Mantel-Haenszel (CMH) statistic adjusting for the effect of randomization strata and disease severity (moderate [IGA=3] or severe [IGA=4]) at Study Baseline; p-values will be calculated from the CMH statistic; and (2) the proportion of responders in each treatment group will be summarized along with pairwise differences and their 95% confidence intervals obtained by normal approximation. The difference in proportions will be calculated within each stratum. The final estimate of the difference in proportions will be a weighted average of these stratum-specific estimates using CMH weights. The CMH weight w_k for stratum k ($k = 1, 2, \dots, K$) is given by,

$$w_k = \frac{\frac{n_{ik} n_{ck}}{n_{ik} + n_{ck}}}{\sum_{j=1}^K \frac{n_{ij} n_{cj}}{n_{ij} + n_{cj}}}$$

where n refers to sample size, the subscript c refers to a comparator group and the subscript i refers to a test group. The difference is estimated as $\hat{d} = \sum_{k=1}^K w_k (\hat{p}_{ik} - \hat{p}_{ck})$, where \hat{p} refers to the estimated relative frequency (or proportion of responders).

Two-sided 95% confidence intervals for the difference (based on a normal approximation) are formed by:

$$\hat{d} \pm 1.96 \sqrt{\sum_{k=1}^K w_k^2 \left(\frac{\hat{p}_{ik}(1 - \hat{p}_{ik})}{n_{ik}} + \frac{\hat{p}_{ck}(1 - \hat{p}_{ck})}{n_{ck}} \right)}$$

In the above formula for the variance of \hat{d} (under the square-root sign), when the number of responders is zero ($x = 0$), then \hat{p} will be replaced by $0.5/(n + 1)$. This change will be made only for calculating the variance of \hat{d} and not anywhere else. Estimates of the

difference in proportions along with the two-sided 95% confidence interval will also be provided for the PF-04965842 200 mg QD group versus the PF-04965842 100 mg QD group. No hypotheses will be tested. In analyses of responders, 95% confidence intervals will be calculated for the estimated proportion of response. The confidence interval is based on the normal approximation (or the Clopper-Pearson exact method when there are no or 100% responders).

For analyses where treatment comparisons are not relevant, only the proportion of responders will be reported along with its 95% confidence interval based on normal approximation (or the Clopper-Pearson exact method when there are no or 100% responders).

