6.3. Secondary Endpoints (Efficacy)

6.3.1. Response Based on (IGA, EASI-50, EASI-75, EASI-90, EASI-100, NRS4 for Severity of Pruritus, SCORAD50 and SCORAD75, IGA + EASI-75)

	All Randomized Subjects	Randomized Subjects Requiring Rescue Treatment	Pre- Randomization Subjects
Summary	Proportion of subjects achieving a response at Weeks 12, 16, 28, 40 and 52	Proportion of subjects achieving a response at Rescue Weeks 2, 4, 8 and 12	Proportion of subjects achieving a response at Weeks 2, 4, 8 and 12
Population	FAS-RA	FAS-RE	FAS-OL
Baseline	Study (see Section 3.4)	Rescue (see Section 3.4)	Study (see Section 3.4)
Statistical Method	CMH and normal approximation as in Section 5.2.1 .	Normal approximation as in Section 5.2.1 .	Normal approximation as in Section 5.2.1 .
Missing Data	Missing values after dropout are defined as “non-response” (see Section 5.3.1)	Missing values after dropout are defined as “non-response” (see Section 5.3.1)	Missing values after dropout are defined as “non-response” (see Section 5.3.1)

6.3.2. Change from Baseline in (Total EASI Score, SCORAD (VAS) Pruritus and Sleep Sub-Scales, PP-NRS for Severity and Percent BSA)

	All Randomized Subjects	Randomized Subjects Requiring Rescue Treatment
Summary	Change from baseline at Weeks 12, 16, 28, 40 and 52	Percent change/Change from baseline at Rescue Weeks 2, 4, 8 and 12
Population	FAS-RA	FAS-RE
Baseline	Study (for Week 12); Randomization (for visits after Week 12) (see Section 3.4)	Rescue (see Section 3.4)
Statistical Method	MMRM as in Section 5.2.2	MMRM as in Section 5.2.2
Missing Data	Use observed data (see Section 5.3.2)	

Change from Study Baseline at Week 12 and its 95% CI will be estimated for each randomized treatment group using an MMRM analysis using data from Weeks 2, 4, 8 and 12. For PP-NRS, data will be included from Days 2 – 15, Weeks 4, 8 and 12.

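### The variance rule for stratified differences in proportions covers strata with no responders but not strata at 100%, so the planned Week 12 intervals are expected to have zero width (minor)

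*SAP*

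**What the plan says.** SAP 5.2.1 tests binary endpoints with the CMH statistic, "adjusting for the effect of randomization strata and disease severity (moderate [IGA=3] or severe [IGA=4]) at Study Baseline". With two age strata and two severity levels this gives four strata. For estimation, "The difference in proportions will be calculated within each stratum" and the stratum differences are averaged with CMH weights. "Two-sided 95% confidence intervals for the difference (based on a normal approximation) are formed by" a formula whose variance sums the squared weight times p(1-p)/n over strata and both arms.

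The section then gives one exception. "when the number of responders is zero", the estimated proportion is replaced by 0.5/(n+1). "This change will be made only for calculating the variance of" the difference. Nothing is said about a stratum in which all subjects respond. For the confidence interval of a single proportion, by contrast, the same section names both extremes: "or the Clopper-Pearson exact method when there are no or 100% responders".

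SAP 6.3.1 applies this method to FAS-RA for the IGA, EASI, pruritus NRS4, SCORAD and IGA + EASI-75 responses, measured from Study Baseline: "Proportion of subjects achieving a response at Weeks 12, 16, 28, 40 and 52". SAP 6.4.2 does the same for PtGA. SAP 2.2 makes IGA 0 or 1 with a reduction of at least 2 points, together with EASI-75, the condition for randomization at Week 12.

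**The concern.** The term p(1-p)/n vanishes at p = 1 just as it does at p = 0. A stratum at 100% then enters the interval as if its response rate were known without error, and the interval is too short by that stratum's share. The SAP guards against this at one end of the scale only, in a trial where every randomized subject is selected to start at the other end.

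What is at stake is the printed interval for secondary binary endpoints. It matters most for 200 mg versus 100 mg, where SAP 5.2.1 provides the difference and its interval and says that no hypothesis is tested, so the interval is the main statement of uncertainty.

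**Working it through.** **Inputs.** From the documents: z = 1.96, the CMH weights, the variance formula and the x = 0 rule (SAP 5.2.1); 200 per arm (SAP 2.2); the visits (SAP 6.3.1). Neither document gives stratum sizes or response rates after randomization. I assume 96/64/24/16 or 110/70/12/8 per arm (two adult strata, then two adolescent strata), the same in both arms, so that the CMH weight reduces to w = n/200.

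**Rules compared.** As written: x = 0 gives p = 0.5/(n+1); x = n is left at p = 1. Mirror rule: in addition, x = n gives p = (n+0.5)/(n+1) = 1 - 0.5/(n+1). Because p(1-p) is symmetric, the mirror rule gives at x = n exactly what the SAP gives at x = 0:

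| n | term at x = 0 | at x = n, as written | at x = n, mirror |
|---|---|---|---|
| 16 | 0.00178 | 0 | 0.00178 |
| 24 | 0.00082 | 0 | 0.00082 |
| 64 | 0.000119 | 0 | 0.000119 |
| 96 | 0.0000534 | 0 | 0.0000534 |

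**Week 12.** All strata are at 100% in both arms. As written, the variance is 0 and the interval is (0, 0). With the mirror rule and 96/64/24/16, each stratum contributes 2 × w² × term. For n = 96 this is 2 × 0.48² × 0.0000534 = 0.0000246. The four contributions sum to 0.0000954, so SE = 0.0098 and the interval is ±0.019. With 110/70/12/8 the SE is 0.0096. The SAP's own rule gives these same values if every stratum has zero responders. The zero width needs no assumed rate; only the corrected width depends on stratum sizes.

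**One near-ceiling example.** Strata 96/64/24/16; 200 mg at 100% throughout; 100 mg at 93/96, 62/64, 24/24 and 16/16 (97.5% overall).
- As written, only the two 100 mg adult strata contribute. In both, p = 0.96875 and p(1-p) = 0.03027. Variance = 0.48² × 0.03027/96 + 0.32² × 0.03027/64 = 0.0000727 + 0.0000484 = 0.0001211. SE = 0.0110 and the interval is (0.003, 0.047).
- The mirror rule adds 0.0000477 for the 200 mg arm and 0.0000232 for the 100 mg adolescents. Variance = 0.0001920, SE = 0.0139 and the interval is (-0.002, 0.052). It is 26% wider and now includes zero.

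**Later visits in general.** Simulation of the SAP formula with strata 110/70/12/8, a common rate across strata and 200,000 trials per row:

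| Rates | Coverage as written | Coverage, mirror rule | Mean SE ratio |
|---|---|---|---|
| 80% v 60% | 94.7% | 94.8% | 1.001 |
| 90% v 70% | 94.7% | 94.8% | 1.003 |
| 95% v 87% | 94.6% | 94.9% | 1.012 |
| 98% v 95% | 94.5% | 95.7% | 1.055 |
| 99.5% v 97.5% | 93.0% | 97.8% | about 1.20 |

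At 95% v 87% some stratum reaches 100% in 92% of trials, yet the width hardly moves. The small strata (12 and 8) carry 10% of the weight, and the weights are squared. At 99% v 98% with 96/64/24/16, coverage is 94.4% as written and 98.3% with the mirror rule.

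**The case against.** A reader might infer that the plan's intervals are generally too narrow. The documents do not support that. SAP 5.3.1 counts rescue and dropout as non-response, so after Week 12 rates fall with both, and below about 95% the shortfall is negligible with coverage close to nominal. The near-ceiling figures depend on rates that neither document supplies.

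A reader might also infer that the x = 0 rule guards the wrong end. It does not. EASI-90, EASI-100, NRS4, SCORAD and PtGA response are not randomization criteria, and for low-rate endpoints zero is the likely extreme. At 20% v 5% with strata 110/70/12/8, 88% of simulated trials contain a zero stratum and none contains a 100% stratum.

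The strongest point concerns Week 12 itself. Everyone has had the same open-label treatment, and blinded dosing starts the day after the visit (protocol Section 5), so the difference is zero by selection and an interval of ±1.9 points tells the reader nothing. SAP 5.2 limits comparisons to where they are relevant. That argues for not comparing arms at Week 12, and I accept it. It does not remove the gap, because SAP 6.3.1 lists Week 12 under the CMH and normal-approximation method, where the stated rule prints (0, 0) and the CMH statistic is undefined.

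Finally, the mirror rule is a convention, not a correction to nominal. At 99.5% v 97.5% it over-covers by more than the present rule under-covers. That stands as a small cost.

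**Conclusion.** Wrong as written, and minor. A stratum at 100% contributes exactly zero variance and SAP 5.2.1 has no rule for it, although the same section treats both extremes for single proportions. At Week 12 the entry rule makes this the expected case in every arm and stratum for the four endpoints tied to randomization, apart from entry deviations or missing data.

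Beyond Week 12 the size depends on assumed stratum sizes and rates: about 1% of width or less below roughly 95% response, about 5% at 98% v 95%, and about 20% at 99.5% v 97.5%. No confirmatory result is touched. The primary and key secondary endpoints are analysed as time to event (SAP 6.1 and 6.2), the binary p-values come from the CMH statistic and do not use this variance, and these endpoints lie outside the test hierarchy (SAP 5.1).

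**What to change.** Two edits to the SAP.

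1. In 5.2.1, keep the x = 0 rule and add: when all subjects in a stratum respond (x = n), the estimated proportion is replaced by (n+0.5)/(n+1), in the variance of the difference only.
2. In 6.3.1, report Week 12 FAS-RA response for IGA, EASI-50, EASI-75 and IGA + EASI-75 descriptively, without between-arm differences or tests.

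The first edit leaves point estimates and p-values unchanged and alters no interval unless a stratum is at 100%. Its cost is one clause and conservative intervals near the ceiling (about 98% coverage at 99% v 98%). The second edit removes only comparisons whose answer is fixed by selection.

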After completing the 12-week rescue period, eligible subjects may enter study B7451015. Subjects discontinuing early from treatment, or who are otherwise ineligible for the LTE study will undergo a 4 week follow-up period in B7451014.

The total study duration if a subject does not flare is 52 weeks (12 weeks open-label treatment + 40 weeks blinded treatment). The maximum study duration is up to 64 weeks. This would only be achieved if a subject flared on the last day of the maintenance treatment period (52 weeks +12 weeks rescue). If subjects do not intend to enroll in the LTE study, the above durations are extended by +4 weeks of an untreated follow-up period.

A full schedule of activities for the study is provided in [Appendix 7](#).

Sample Size Determination

A total of 600 subjects with 200 receiving PF-04965842 200 mg QD, 200 receiving PF-04965842 100 mg QD, and 200 receiving placebo (1:1:1 randomization) will provide 94% power to detect a ratio of median time to flare of at least 1.5 times between either dose of PF-04965842 (200 mg or 100 mg) and placebo. The Type I error rate is set at 5% (2-sided). Assuming that about 44% of subjects would meet the protocol-defined criteria to be a responder at Week 12, (based on prior data), approximately 1370 subjects would need to enter the open label run-in period of the study to ensure that 600 subjects are available for randomization.

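### Single-group response rates get a normal-approximation interval unless exactly 0% or 100% respond, so intervals within three subjects of the boundary pass 0% or 100% and coverage close to it can fall to about 85%

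*SAP*

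**What the plan says.** SAP section 5.2.1 sets two kinds of interval for binary endpoints. One is for the stratified difference between arms and is not at issue. The other is for each group's own rate: "95% confidence intervals will be calculated for the estimated proportion of response", with the method given as "The confidence interval is based on the normal approximation (or the Clopper-Pearson exact method when there are no or 100% responders". Where there is no treatment comparison, which SAP section 5.2 says is the case for FAS-OL and FAS-RE, the rule is repeated and "only the proportion of responders will be reported along with its 95% confidence interval based on normal approximation", again with the exact method only at no or all responders.

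The single-group formula is not written out. The Wald form, p ± 1.96 × √(p(1−p)/n), is the ordinary reading of normal approximation and matches the formula that the section does write out for the difference. The SAP does not truncate limits at 0% or 100% and has no rule for low counts. Its substitution of 0.5/(n + 1) for a zero proportion is confined to the variance of the difference.

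The rule applies to the secondary responder endpoints of section 6.3.1, where the FAS-RA row reads "Proportion of subjects achieving a response at Weeks 12, 16, 28, 40 and 52", and to the PtGA response in section 6.4.2.

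**The concern.** By changing method at 0% and 100%, the SAP accepts that the normal approximation breaks down at the boundary. It breaks down beside the boundary too, and there the rule keeps it. Two consequences follow for a results table: limits that are impossible as proportions, and a lower limit that gets worse when the last non-responder becomes a responder. A third is less visible: an interval labelled 95% that covers less often than that.

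The design makes the upper boundary reachable. Only subjects who meet both the IGA and the EASI-75 criteria at Week 12 are randomized, and FAS-RA rates are tabulated from Week 12 onward. FAS-RA keeps every randomized and dosed subject, whereas the per-protocol set separately requires that the randomization criteria were met. A few subjects randomized in error would therefore put a Week 12 rate just below 100%. In FAS-RE the group's interval is the only inference reported.

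**Working it through.** **Inputs from the documents**
- 200 subjects per arm: "A total of 600 subjects with 200 receiving PF-04965842 200 mg QD, 200 receiving PF-04965842 100 mg QD, and 200 receiving placebo (1:1:1 randomization" (SAP section 2.2).
- Run-in set: "approximately 1370 subjects would need to enter the open label run-in period of the study to ensure that 600 subjects are available for randomization", on a responder rate of 44% (same section). Check: 600/0.44 = 1363.6, which agrees with the rounded 1370.
- Interval rule: SAP section 5.2.1, as above.

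**Assumed, because the documents do not give them:** true response rates after randomization and under rescue (scanned below), and the size of FAS-RE (100, for illustration).

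**1. Limits with n = 200**

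At 199/200, √(0.995 × 0.005/200) = 0.00499, and 0.995 ± 1.96 × 0.00499 = 0.9852 to 1.0048. At 200/200 the rule switches to the exact method, with lower limit 0.025^(1/200) = 0.9817.

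| Responders | SAP rule | Clopper-Pearson throughout |
|---|---|---|
| 200/200 | 98.17% to 100% | 98.17% to 100% |
| 199/200 | 98.52% to 100.48% | 97.25% to 99.99% |
| 198/200 | 97.62% to 100.38% | 96.43% to 99.88% |
| 197/200 | 96.82% to 100.18% | 95.68% to 99.69% |
| 196/200 | 96.06% to 99.94% | 94.96% to 99.45% |

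The upper limit exceeds 100% when the number of non-responders m satisfies m < 1.96² × n/(n + 1.96²). For n = 200 this is 3.84 × 200/203.84 = 3.77, hence m = 1, 2 or 3. The same three counts fail at n = 30, 50, 100, 600 and 1370. Near 0% the picture is mirrored: 1/200 gives −0.48% to 1.48%.

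**2. Exact coverage**

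Coverage at a true rate p is the sum of the Binomial(n, p) probabilities of all counts whose interval contains p.

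Take n = 200 and p = 98.5%. The intervals that contain p are those for 192 to 198 responders and for 200. The count of 199 misses, because its lower limit is 98.52%. The probability of exactly one non-responder is 200 × 0.015 × 0.985^199 = 0.148, and that of nine or more is 0.0035. Coverage is 1 − 0.148 − 0.0035 = 84.8%. The single misplaced interval at 199/200 accounts for nearly all of the loss.

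| True rate, n = 200 | SAP rule | Clopper-Pearson |
|---|---|---|
| 90% | 92.7% | 96.7% |
| 95% | 92.6% | 96.7% |
| 96% | 89.8% | 97.2% |
| 97% | 93.3% | 96.5% |
| 97.5% | 87.4% | 98.1% |
| 98% | 90.8% | 96.2% |
| 98.5% | 84.8% | 98.9% |
| 99% | 99.9% | 98.4% |

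Over a grid from 90% to 99%, the SAP rule averages 93.0%, with its minimum of 84.4% at 98.52%. Clopper-Pearson averages 96.8% and never falls below 95%.

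**3. Other analysis sets**
- FAS-OL, n = 1370: 94.7% coverage at a true rate of 44%, and 95.1% at 63.7%, the Phase 2b EASI-75 rate on 200 mg (protocol section 1.2.4). On a 0.05-point grid above 50%, coverage is below 90% only at 99.65% and 99.75%, with the mirror image near 0.3%.
- FAS-RE, n assumed 100: 87.7% at a true rate of 95%, and 85.0% at 97%.

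**The case against.** The strongest reply is that the low coverages are troughs. Coverage of an interval for a count oscillates: at n = 200 it is 84.8% at a true rate of 98.5% but 99.9% at 99% and 93.3% at 97%. This stands. A reader who saw only the troughs might infer that about 85% is typical near the boundary, and the full set of rates does not support that.

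A reader might also infer that rates in the failing zone are to be expected because the trial is enriched for responders. The documents do not say so. They give no response rates after randomization or under rescue, and SAP section 5.3.1 counts rescued subjects and dropouts as non-responders at later visits, which pulls FAS-RA rates away from 100%. To sit at the worst point after Week 12, an arm could lose only about 1.5% to failure, rescue and dropout together. At Week 12 itself, correct randomization gives exactly 100%, where the SAP already uses the exact method; and because that rate is a selection criterion, coverage there means little. This stands as well, but it does not remove the impossible limits or the reversal if one to three subjects per arm are randomized in error.

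A third inference would be that the run-in results suffer, since their only inference is this interval. At about 1370 subjects and the rates in the documents they do not.

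Finally, no decision depends on these intervals. That is correct and sets the weight of the point. It does not make the stated rule sound: nothing elsewhere in the SAP truncates or repairs the limits.

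**Conclusion.** The point holds as a minor defect in a descriptive method. With 200 per arm, the limits leave the 0% to 100% range when there are 1 to 3 non-responders or 1 to 3 responders, and the lower limit reverses between 199/200 and 200/200. These are arithmetic facts about the rule, given the Wald reading of normal approximation. For true rates of 90% to 99%, coverage averages about 93%; about 85% is the worst case, near 98.5%.

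How often the zone is reached is an assumption. It can be reached in FAS-RA arms, for example in Week 12 rates after a few randomization errors, and possibly in a small FAS-RE. FAS-OL is essentially unaffected. The log-rank tests of the primary and key secondary endpoints, the CMH p-values and the intervals for differences are unchanged. The change is worth making because it is cheap.

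**What to change.** In both places in SAP section 5.2.1, state that the 95% confidence interval for each single-group proportion of responders uses the Clopper-Pearson method at all response rates, and delete the switch at 0% and 100%. One method should be named, not a choice. Wilson would be less conservative, but at n = 200 its coverage also falls to about 85% for true rates around 99.9%.

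Align the labels that would otherwise describe a method no longer used: the FAS-RE and FAS-OL columns of the table in section 6.3.1, and the corresponding rows of Appendix 1. In the FAS-RA entries, including section 6.4.2, the normal-approximation label can stay if it is tied to the difference between arms.

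The cost is a short text edit and one program option. The intervals become slightly conservative: at 196/200 the width goes from 99.94 − 96.06 = 3.88 points to 99.45 − 94.96 = 4.49 points. Sample size and hypothesis tests are untouched.

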5.2.2. Analyses for Longitudinal Continuous Data

Mixed-effect, repeated measures (MMRM) models will be used. Fixed effects for visit, treatment group, treatment-by-visit interaction (where treatment comparisons are relevant), disease severity at Study Baseline and randomization stratification factor will be included in the model. Visit will be modeled as a categorical covariate. Unstructured covariance matrix will be assumed for the model errors. Compound symmetry covariance matrix will be used if the model with unstructured covariance doesn't converge.

When modeling the change from baseline values, the variable for visit will start with the first post-baseline visit, and the actual baseline value will be included as a covariate. At each visit, estimates of least square mean (LSM) values and the pairwise LSM differences between the treatment groups will be derived from the model. The corresponding p-values and 95% confidence intervals will also be derived from the model.

For analyses where treatment comparisons are not relevant, the MMRM model will not have treatment as a factor and only estimates of the LSM values along with their 95% confidence intervals by visit will be reported.

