5.3.2. Continuous Endpoints

For longitudinal continuous endpoints based on the FAS-OL or FAS-RE analysis sets, assuming that the missing data mechanism is missing at random (MAR), the data will be analyzed based on the full likelihood using a linear mixed-effect model with repeated measures for these continuous variables (see [Section 5.2.2](#)). This model will yield unbiased estimates and valid inferences in the presence of a missing data mechanism that is MAR.

In the context of analyses based on the FAS-RA analysis set, subjects requiring to enter the rescue phase of the study are considered dropouts from randomized treatment along with discontinuation from study during double blind period due to any reason. This implies that outcome values after this intercurrent event will be considered missing data. The determination of a protocol-defined flare event (or dropout) is based on past and current values for the total EASI score and the IGA score prior to dropout and not influenced by future (unobserved) values of these assessments beyond dropout. So the mechanism for such a dropout, conditional on the past and current values for total EASI score and IGA score, may be considered MAR. Therefore, the data may be analyzed based on the full likelihood using a linear mixed-effect model with repeated measures for these continuous variables (see [Section 5.2.2](#)). This model will yield unbiased estimates and valid inferences in the presence of a missing data mechanism that is MAR.

In general, for non-PRO continuous endpoints measured longitudinally, missing values post-baseline will not be imputed explicitly. For the continuous PRO variables such as pruritus NRS, DLQI/CDLQI, POEM, PSAAD and HADS, rules (if any) suggested by the developers of these instruments will be followed in calculating the outcome value in the presence of missing data. If these rules are not enough for imputing a value, then the missing values will be handled in the same way as other non-PRO variables.

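### If the unstructured MMRM does not converge, the SAP's direct fallback to compound symmetry can distort interval widths and, in the post-randomization comparisons, bias late treatment differences

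*SAP*

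**What the plan says.** SAP 5.2.2 sets the default, "Unstructured covariance matrix will be assumed for the model errors", and then the only alternative: "Compound symmetry covariance matrix will be used if the model with unstructured covariance" fails to converge. Inference is model-based: "The corresponding p-values and 95% confidence intervals will also be derived from the model". No empirical (sandwich) standard error is named.

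SAP 5.3.2 treats entry into rescue as dropout in the FAS-RA analyses, argues that this dropout is MAR because flare is determined by observed EASI and IGA, and concludes: "This model will yield unbiased estimates and valid inferences in the presence of a missing data mechanism that is MAR". It attaches no condition on the covariance. The SAP plans a tipping-point analysis for time to flare, but no sensitivity analysis for the continuous endpoints.

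The models governed by this rule differ in size:

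- **Post-randomization, FAS-RA (SAP 6.3.2, 6.4.1).** The summary row reads "Change from baseline at Weeks 12, 16, 28, 40 and 52". Week 12 is estimated separately from run-in data, which leaves Weeks 16, 28, 40 and 52.
- **Run-in, for Week 12.** Most endpoints use Weeks 2, 4, 8 and 12. The itch scale uses many more occasions: "For PP-NRS, data will be included from Days 2 – 15, Weeks 4, 8 and 12". PSAAD uses twelve weekly values and is collected in selected countries only. Estimates are per randomized group.
- **Rescue, FAS-RE.** Rescue Weeks 2, 4, 8 and 12, with no treatment comparison.

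**The concern.** Compound symmetry imposes one variance on all visits and one correlation on all pairs of visits. Subjects are randomized only after reaching IGA 0 or 1 and EASI-75, then continue on 200 mg, 100 mg or placebo. Spread that grows after Week 12 and correlation that weakens with time apart are plausible, though the documents give no SD or correlation by visit.

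Two things follow if the fallback is used when variances differ. First, a pooled variance gives the wrong standard error at individual visits. Second, when subjects leave because of observed outcomes, a likelihood analysis under MAR relies on the covariance model to carry information from observed to missing visits. If that model is wrong, and dropout differs by arm, the treatment difference at late visits can be biased. The assurance in SAP 5.3.2 would then not hold for that table.

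**Working it through.** **The plan's own figure.** None exists on this point: no SD, correlation or precision is stated for any MMRM endpoint. All SDs, correlations and mean paths below are therefore assumptions.

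**Model size.** Unstructured parameters = k(k+1)/2 for k occasions.
- Post-randomization: 4 × 5/2 = 10.
- PSAAD run-in: 12 × 13/2 = 78.
- PP-NRS run-in: 14 days + 3 visits = 17 occasions if each day is a level, so 17 × 18/2 = 153.

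**Complete data.** With n per arm, the compound-symmetry SE of a difference is sqrt(2 × mean variance/n) at every visit. The correct SE is sqrt(2 × visit variance/n). The ratio r is sqrt(mean variance/visit variance).
- Equal variances give r = 1 whatever the correlation. With SD 8 and 200 per arm, sqrt(2 × 64/200) = 0.800. Simulation with decaying correlation gave 0.798 (compound symmetry) against 0.800 (unstructured).
- With SD rising from 5 to 9.5, the simulated ratio of model SE to empirical SE was 1.59 at Week 16 and 0.81 at Week 52.
- For the 17-occasion run-in model, assuming variance grows from 2–4 up to 6, the Week 12 SE is 8% to 16% too small. Coverage is 2Φ(1.96r) − 1: 93% at r = 0.92 and 90% at r = 0.84. If Week 12 variance is instead below the mean, r exceeds 1 and the interval is too wide.

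**Flare level implied by the design.** Schoenfeld events for 94% power at a median ratio of 1.5 (exponential): 4 × (1.960 + 1.555)²/(ln 1.5)² = 49.42/0.1644 = 301 of 400 per comparison, about 75%. That corresponds to about 82% flare on placebo and 68% on active. The documents state no event rate.

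**Simulation.** Two arms of 200, Weeks 16/28/40/52, 300 replicates. Data after the first visit with EASI at least 15 above Week 12 were removed (the threshold in the worked example of SAP 3.1; the IGA part was not modelled). Correlation decays with time apart except in row B. Week 52 results, CS = compound symmetry, UN = unstructured:

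| Scenario (flare placebo vs active) | True diff. | CS bias | CS SE ratio | CS cover | UN bias | UN cover |
|---|---|---|---|---|---|---|
| A. Complete data, SD 5 to 9.5 | – | +0.02 | 0.81 | 90.3% | +0.02 | 95.3% |
| B. CS true (67% vs 23%) | 9.5 | +0.02 | 0.98 | 94.3% | +0.01 | 95.0% |
| C. Flat SD (65% vs 22%) | 9.5 | −0.12 | 0.87 | 91.3% | +0.04 | 91.3% |
| D. SD 5 to 9.5 (63% vs 22%) | 9.5 | −1.55 | 0.73 | 50.7% | +0.04 | 92.0% |
| E. SD 5 to 9.5 (72% vs 59%) | 3.0 | −0.69 | 0.72 | 76.3% | +0.06 | 94.0% |
| F. SD 5 to 9.5, no effect (40% vs 40%) | 0 | −0.03 | 0.72 | 84.0% | −0.03 | 93.0% |
| G. SD 7 to 8.5, correlation 0.9 per 12 weeks (57% vs 17%) | 9.5 | −0.79 | 0.86 | 78.7% | −0.01 | 93.7% |

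Relative bias: D 1.55/9.5 = 16%; E 0.69/3.0 = 23%; G 0.79/9.5 = 8%. Row E is closest to the design-implied flare level. In row F the type I error is 100 − 84 = 16%, against 7% unstructured. Monte Carlo error is about 0.05 to 0.07 on bias and 1.3 to 2.9 points on coverage. In rows C to F the unstructured SE ratio at Week 52 was itself about 0.9, so part of the undercoverage there is not due to compound symmetry.

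A separate simulation (SD 4 to 8, lag-1 correlation 0.7, 240 runs) agrees. Compound symmetry gave −4.9 against a true −6.0 (1.1/6.0 = 18% toward zero) with about 60% coverage; unstructured gave −6.05 and about 94%.

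**Candidate repairs, Week 52.**
- CS with sandwich SE: coverage rises to 93.7% in F, but only to 88.3% in E and 67.0% in D, with the bias unchanged.
- Heterogeneous AR(1): bias +0.05 and coverage 92.7% in D, +0.08 and 93.3% in E. When compound symmetry is true (B), it is biased by −0.76 with 88.3% coverage.
- Heterogeneous Toeplitz, run only in the separate simulation under a non-AR true correlation: coverage about 88%, against about 42% for compound symmetry.

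**The case against.** The strongest reply is that the harm and the trigger sit in different models. The bias arises in the four-visit randomized comparisons, which have 10 covariance parameters and about 600 planned subjects and should converge. The models that might fail, PP-NRS and PSAAD in the run-in, precede randomization. Everyone in them was on open-label 200 mg, FAS-RA subjects had reached Week 12, and only per-group Week 12 estimates are planned. This stands, and it is why the point is minor.

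The variance pattern is also assumed. The drug's terminal half-life is a few hours (Protocol 1.3) and the first randomized visit is four weeks after withdrawal, so much of the divergence could precede Week 16. Selection at Week 12 for IGA 0 or 1 and EASI-75 could compress the spread there, which would make run-in intervals too wide. This stands too: the direction of the run-in error is not established.

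Finally, SAP 5.3.2 points to 5.2.2, whose default is unstructured, and for that default the MAR claim is reasonable. True, but the same sentence also covers a table produced under the fallback.

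A reader might infer that compound symmetry cannot hold here, or that every MMRM using it has wrong intervals. The documents do not support either: they give no variances, and compound symmetry did about as well as unstructured with equal SDs (the complete-data check and row C) and when it was the true structure (row B). A reader might also infer that every fallback model pulls a Week 52 difference toward zero. The run-in and rescue models contain no Week 52 difference, and there was essentially no bias with complete data or no treatment effect.

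**Conclusion.** The gap is real but conditional, and it warrants a cheap improvement rather than a required change. Two conditions must meet: the unstructured fit fails, and variances differ by visit. Interval widths are then wrong, by an SE ratio of 1.59 at Week 16 and 0.81 at Week 52 in the complete-data example. For a biased difference, outcome-driven dropout must also differ by arm, which among these models is possible only in the FAS-RA post-randomization comparisons. The simulated 8% to 23% bias toward zero and 51% to 84% coverage rest on assumed growing SDs and decaying correlation and should be read as a range of what could happen, not as a forecast. Nothing in the documents indicates that convergence will fail.

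The primary and key secondary endpoints use the stratified log-rank test and are unaffected. The MMRM endpoints lie outside the gatekeeping sequence and are tested at nominal 5% (SAP 5.1).

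**What to change.** Before unblinding, replace the fallback sentence in SAP 5.2.2 with an ordered list, stopping at the first structure that converges:

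1. Unstructured, retried with other starting values.
2. Heterogeneous Toeplitz.
3. Heterogeneous AR(1), or a spacing-aware version where visits are unevenly spaced, as in the run-in and rescue models.
4. Heterogeneous compound symmetry.
5. Plain compound symmetry, last.

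Use empirical (sandwich) standard errors for every structure other than unstructured, and report the structure used in each table. In SAP 5.3.2, add that validity under MAR also requires an adequate covariance model.

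The cost is a short SAP edit and a few lines of code, and nothing changes where the unstructured model converges. Sandwich errors are somewhat noisier in small subsets and do not remove bias, and a restricted structure such as heterogeneous AR(1) can itself be biased if wrong. The list therefore reduces the problem without eliminating it.
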